7.2 Alzheimer's Disease Cooperative Study - Clinician's Global Impression of Change (ADCS-CGIC)

The ADCS-CGIC ([Schneider et al., 1997](#)) is a validated scale for assessing clinically relevant global change in patients with dementia, which was originally developed for patients with AD. The ADCS-CGIC consists of an organized but unstructured assessment of the patient's function and mental status, a caregiver interview, and a standardized set of questions. Depending on a patient's level of impairment, raters consider several domains (e.g., global cognition, attention and wakefulness, psychiatric symptoms) in formulating a CGIC rating. The assessments are integrated in a 7-point categorical scale that gives a global rating of change in symptoms from a baseline level. A score of 1 = marked improvement; 2 = moderate improvement; 3 = minimum improvement; 4 = no change; 5 = minimum worsening; 6 = moderate worsening; and 7 = marked worsening. The ADCS-CGIC will be collected at Week 16 (or at Early Termination prior to Week 16, if applicable), and may be performed at any point during the study visit based on clinical interview by an Investigator who is blinded to the cognitive evaluations.

Only Sponsor-accepted raters may administer the ADCS-CGIC in accordance with the requirements for background, experience in a research setting and training in accordance with the rater experience form.

7.3 Alzheimer's Disease Assessment Scale - Cognitive Subscale (ADAS-cog) (Revised 10OCT13)

The ADAS-cog ([Mohs et al., 1988; Mohs et al., 1997](#)) is the cognitive subscale of the Alzheimer's Disease Assessment Scale (ADAS), a validated instrument designed to measure the severity of the most prominent symptoms of dementia in patients with AD. The ADAS-cog subscale consists of 11 tasks measuring alterations of memory, language, praxis, attention and other cognitive abilities which comprise the core symptoms of AD and PDD. **This study utilizes the original ADAS-cog and does not include the supplemental maze and number cancellation tasks.** The ADAS-cog will be administered to randomized patients in this study at Baseline (before the initiation of dosing) and at Week 16 (or at Early Termination prior to Week 16, if applicable).

Only Sponsor-accepted raters may administer the ADAS-cog in accordance with the requirements for background, experience in a research setting and training in accordance with the rater experience form.

7.4 Brief Penn Daily Activity Questionnaire (PDAQ)

The PDAQ ([Weintraub et al., 2013](#)) is a 15-item questionnaire selected by an expert panel from a bank of 50 items. The PDAQ represents a new comprehensive instrument comprised of item-response theory scaled items for rating daily cognitive function in patients with PD. The questionnaire correlates highly with global cognitive performance in PD patients and shows good

discriminant validity across stages of cognitive impairment. The informant version of the PDAQ will be administered to the caregiver of randomized patients in this study at Baseline (before the initiation of dosing) and at Week 16 (or at Early Termination prior to Week 16, if applicable).

Only Sponsor-accepted raters may administer the Brief PDAQ in accordance with the requirements for background, experience in a research setting and training in accordance with the rater experience form.

7.5 Parkinson's Disease-Adapted Scale for Assessment of Positive Symptoms (SAPS-PD) (2013 Shortened Version)

The SAPS-PD is the Parkinson's disease-adapted version of the Scale for Assessment of Positive Symptoms ([Andreasen, 1984](#)) tailored to PDD. A shortened version of the SAPS-PD has recently been developed ([Voss et al., 2013](#)). The 2013 shortened version of the SAPS-PD will be administered to randomized patients in this study at Baseline (before the initiation of dosing) and at Week 16 (or at Early Termination prior to Week 16, if applicable).

Only Sponsor-accepted raters may administer the SAPS-PD in accordance with the requirements for background, experience in a research setting and training in accordance with the rater experience form.

7.6 Neuropsychiatric Inventory (NPI) (Version 12)

The NPI ([Cummings et al., 1994](#)) is a copyrighted validated instrument to assess dementia-related behavioral symptoms. The NPI originally examined 10 sub-domains of behavioral functioning: delusions, hallucinations, agitation/aggression, dysphoria, anxiety, euphoria, apathy, disinhibition, irritability/lability, and aberrant motor activity. Sub-domains subsequently added include night-time behavioral disturbances and appetite/eating abnormalities ([Cummings, 1997](#)), as well as a caregiver distress scale ([Kaufer et al., 1998](#)). Due to its wide variety of domains compared to dementia measures, the NPI is used to screen for multiple types of dementia in addition to that caused by AD. The NPI will be reported by the subject's caregiver at Baseline (before the initiation of dosing) and at Week 16 (or at Early Termination prior to Week 16, if applicable).

Only Sponsor-accepted raters may administer the NPI in accordance with the requirements for background, experience in a research setting and training in accordance with the rater experience form.

A copy of the NPI is included in [Appendix 14.6](#).

7.7 Scales for Outcomes in Parkinson's Disease-Sleep Scale (SCOPA-SLEEP)

The SCOPA-SLEEP ([Marinus et al., 2003](#)) is a validated instrument to evaluate nighttime sleep and daytime sleepiness developed for research in patients with PD, a population that frequently experience sleep disturbances. The SCOPA-SLEEP consists of two scales, one that evaluates nighttime sleep and one that assesses daytime sleepiness.

Only Sponsor accepted raters may administer the SCOPA-SLEEP in accordance with the requirements for background, experience in a research setting and training in accordance with the rater experience form.

A copy of the SCOPA-SLEEP is included in [Appendix 14.5](#).

7.8 Montreal Cognitive Assessment (MoCA) (Original v7.1, Alternates v7.2 and v.7.3)

The MoCA ([Nasreddine et al., 2005](#)) is a validated brief screening instrument for cognitive dysfunction. The MoCA assesses the cognitive domains of attention and concentration, executive functions, memory, language, visuoconstructional skills, conceptual thinking, calculations, and orientation. The MoCA takes approximately 10 minutes to administer by a trained clinician and must be administered in the local language and scored by a trained clinician. The maximum score is 30; a score of 26 or above is considered normal. The MoCA has validated translations in many languages [<http://www.mocatest.org>].

Only Sponsor accepted raters may administer the MoCA in accordance with the requirements for background, experience in a research setting and training in accordance with the rater experience form.

Subjects may be given any version of the MoCA at the Screening Visit as long as they have NOT received the same MoCA version clinically within the last 3 months. A different version of the MoCA should be used at the Week 16 or Early Termination visit (if applicable). The MoCA version used at a study visit should be accurately documented in Source Document and within the EDC for each visit.

Re-screening: In cases where the subject screen fails due to the MoCA score being out of the required inclusionary range at the Screening Visit, the subject may be re-screened if the subject's score was **> 23**; a minimum of one month must have passed since their original MoCA assessment. If the subject's MoCA score was **< 10**, they must have had a change in therapy or intervention that (in the opinion of the Site Investigator) may have improved the subject's cognitive status. Subjects who move forward with a re-screen must be evaluated using a different MoCA version (7.1, 7.2 or 7.3) than was used at the original Screening Visit, and subjects may be re-screened only once.

7.9 Unified Parkinson's Disease Rating Scale (UPDRS)

The UPDRS ([Fahn et al., 1987](#)) is a scale that was developed as an effort to incorporate elements from existing scales to provide a comprehensive but efficient and flexible means to monitor PD-related disability and impairment.

The scale itself has four components, largely derived from preexisting scales that were reviewed and modified by a consortium of movement disorders specialists (Part I, Mentation, Behavior and Mood; Part II, Activities of Daily Living; Part III, Motor Examination; Part IV, Complications of Therapy). One of the core advantages of the UPDRS is that it was developed as a compound scale to capture multiple aspects of PD. It assesses both motor disability (Part II: Activities of Daily Living) and motor impairment (Part III: Motor Examination). In addition, Part I addresses mental dysfunction and mood, and Part IV assesses treatment-related motor and non-motor complications. Of all available clinical scales for the assessment of Parkinsonian motor impairment and disability, the UPDRS is currently the most commonly used.

Patients with levodopa-related end-of-dose motor fluctuations will be instructed to have already taken their normally scheduled dose of levodopa and their study drug prior to arriving at the study site in order to have their UPDRS Part III evaluated in ON (within approximately 2 to 3 hours after taking their levodopa dose). UPDRS in ON will be measured at a time representative of the ON state in that patient, not in “best” ON. UPDRS Part III in OFF will be not be evaluated.

Only Sponsor accepted raters may administer the UPDRS subscales in accordance with the requirements for background, experience in a research setting and training in accordance with the rater experience form.

A copy of the UPDRS is included in [Appendix 14.4](#).

7.10 Columbia-Suicide Severity Rating Scale (C-SSRS) (Revised 14JAN09)

Suicidality will be assessed by trained study personnel using the C-SSRS ([Posner et al. 2011](#)). The C-SSRS is a copyrighted standardized suicidal rating system conducted by a certified rater. The interview measures presence of suicidality and consists of four categories: suicide ideation, intensity of ideation, suicidal behavior and answer for actual attempts only. This scale will be used for screening as well as to assess for the occurrence of any suicidal ideation and/or behavior during the study.

Only Sponsor accepted trainers may administer the C-SSRS in accordance with the requirements for background, experience in a research setting and training in accordance with the rater experience form.

7.11 Laboratory Tests

The laboratory tests listed below (**Table 5**) are to be performed and analyzed as outlined in the Schedule of Events/Evaluations (**Table 1**).

Sample collection kits and the laboratory procedures manual with detailed sample processing and shipping instruction will be provided by the accredited central laboratory.

All laboratory samples will be destroyed upon authorization by the Sponsor or Sponsor's designee, at the finalization of the clinical study report.

The following laboratory parameters will be measured:

Table 5: Laboratory Measurements

Hematology	Chemistry	Thyroid ^b	Urinalysis ^c
basophils	calcium	TSH	protein
eosinophils	chloride	free T ₃	glucose
lymphocytes	sodium	free T ₄	pH
neutrophils	potassium		blood
monocytes	albumin		ketones
hemoglobin	phosphate		specific gravity
hematocrit	glucose		
platelet count	urea/BUN		
RBC count	bicarbonate		
WBC count	uric acid		
	total protein		
	creatinine		
	creatinine phosphokinase with automatic troponin-I and CK-MB if value > 2x the ULN		
	AST		
	ALT		
	ALP		
	GGT		
	total bilirubin ^a		
	LDH		
	total cholesterol		
	serum FSH (at Screening, for female patients who are not surgically sterile and are postmenopausal)		
	urine hCG (for female patients of childbearing potential)		

ALP, alkaline phosphatase; ALT, alanine transaminase; AST, aspartate transaminase; BUN, blood urea nitrogen; CK-MB, creatine phosphokinase-MB fraction; FSH, follicle stimulating hormone; GGT, gamma-glutamyl transpeptidase; hCG, human chorionic gonadotropin; LDH, lactate dehydrogenase; pH, reverse logarithmic representation of relative hydrogen proton (H⁺) concentration; RBC, red blood cell; T₃, triiodothyronine; T₄, thyroxine; TSH, thyroid stimulating hormone; ULN, upper limit of normal; WBC, white blood cell.

^a Conjugated and unconjugated.

^b Assessed at Screening only.

^c If urine dipstick is positive for leukocytes, protein, or erythrocytes, a microscopic evaluation and culture will be performed.

7.11.1 Hormones (Serum FSH and Urine HCG)

Follicle stimulating hormone (FSH) levels will be determined at Screening for all women who are not surgically sterile and are postmenopausal (at least one year absence of vaginal bleeding

or spotting). Postmenopausal status will be confirmed by an FSH level greater than or equal to 40 mIU/mL or 40 IU/L.

Urine human chorionic gonadotropin (hCG) pregnancy test will be performed for women of childbearing potential, at Screening and during the study as indicated in **Table 1**, Schedule of Events/Evaluations.

7.11.2 Hematology

Hematology tests will consist of hemoglobin, hematocrit, red blood cell count, white blood cell count and differential, and platelet count, at Screening and during the study as indicated in **Table 1**, Schedule of Events/Evaluations.

7.11.3 Chemistry

Serum chemistry tests will consist of aspartate aminotransferase (SGOT/AST), alanine aminotransferase, (SGPT/ALT), gamma-glutamyl transpeptidase (GGT), alkaline phosphatase (ALP), lactate dehydrogenase (LDH), total bilirubin (conjugated and unconjugated), albumin, creatinine, urea/BUN, bicarbonate, uric acid, total protein, sodium, chloride, potassium, calcium, phosphate, glucose, cholesterol, and creatine phosphokinase (CK), TSH, free T₃ and T₄, at Screening and during the study as indicated in **Table 1**, Schedule of Events/Evaluations.

7.11.4 Thyroid Function

Thyroid function tests will consist of thyroid stimulating hormone (TSH), free T₃ and free T₄, at Screening.

7.11.5 Urinalysis

Urinalysis will include specific gravity, pH, ketones, blood, protein, and glucose, at Screening and during the study as indicated in **Table 1**, Schedule of Events/Evaluations. If an urine dipstick is positive for leukocytes, protein or erythrocytes, a microscopic evaluation will be performed.

7.12 Blood Sampling for Bioanalytical Analysis

Blood samples will be collected for determination of SYN120 plasma concentrations [REDACTED] [REDACTED] Baseline (before the initiation of dosing), at Weeks 4, 8 and 16, at Early Termination (if applicable), and at unscheduled visits (optional). For each collection, the time of sampling and of the most recent IMP dosing prior to sampling will be recorded.

Specific procedures for blood sample collection, plasma processing, storage, shipping, and analysis will be provided in the Central Laboratory Procedures Manual.

7.13 Pharmacogenetic Substudy (Optional)

Patients will be offered the option to participate in a pharmacogenetic substudy. Exploratory pharmacogenetic analyses are planned as a substudy with the objective of identifying inherited genetic factors which predict differential treatment response or intolerance to SYN120. Genetic polymorphisms related to the serotonin system (5HT6 and 5HT2a receptors) will be characterized. Other genetic features related to [REDACTED] Parkinson's disease and cognition may also be tested. The intent is to develop a better understanding of Parkinson's disease dementia and how patients respond to SYN120.

Blood samples will be taken for pharmacogenetic assessment from each patient who agrees, in writing, to participate in these exploratory assessments. A separate section on the ICF regarding the pharmacogenetic substudy will be provided. Patients who indicate on the ICF that they agree to the pharmacogenetic assessment will be eligible for extra blood collection and inclusion in pharmacogenetic analyses. A single blood sample will be collected per patient (approximately 10 ml) at Baseline or at the next possible visit.

A separate lab instruction will be provided with detailed information on sample collection, handling, and shipment for all pharmacogenetic assessments. The sample collection data must be entered on the sample collection CRF (eCRF) page.

Blood samples will be processed, DNA extracted, and samples stored [REDACTED]
[REDACTED] Samples may be shared with other investigators [REDACTED]
[REDACTED] Samples will be stored for up to 10 years. Participants may withdraw consent to use their samples at any time, in which case their samples and any derived biospecimens will be destroyed. Samples will be identified only by anonymous study ID number with linked phenotypic information gathered in the study.

7.14 Blood Pressure and Pulse

A full set of BP and pulse measurements will be obtained at Screening (3 sets) and during the study (1 set) as indicated in **Table 1**, Schedule of Events/Evaluations. Blood pressure and pulse rate should be obtained in a quiet room at a comfortable temperature, with the patient's arm unconstrained by clothing or other material. A full set of measurements consists of supine BP and pulse followed by standing BP and pulse. If repeats are performed for either supine or standing BP, the full set (BP and pulse) should be repeated after 5 minutes supine rest (i.e., supine followed by standing measurements). The measurements will be obtained with the appropriate cuff size from the non-dominant arm. All measurements will be obtained from the same arm and, if possible with the same cuff, using an automatic instrument with a digital readout, throughout the study. The automatic cuff should be placed on the designated arm at least 5 minutes prior to collection. Measurements will be made after a minimum of 5 minutes rest in the supine position. Patients will then stand up for 1 and 3 minutes, and a standing measurement

will be obtained. The 3 sets of readings collected during the Screening Visit should be taken approximately 10 minutes apart.

Supine and standing systolic and diastolic BP and pulse rate will be recorded at the nominal time points specified in **Table 1**, Schedule of Events/Evaluations. If for any reason (e.g., dyskinesia) an accurate reading cannot be obtained, collect the measurement as close to the nominal time point as feasible and record the date and time of collection.

7.15 Physical and Neurological Examination

Physical examination including neurological examination will be collected at Screening and during the study as indicated in **Table 1**, Schedule of Events/Evaluations. Physical examination includes evaluation of the heart, lungs, abdomen, extremities, and skin. Neurological exam will consist of assessment of the cranial nerves (I-XII), sensory and motor system functions and reflexes.

7.16 Twelve-lead Electrocardiogram

Resting supine 12-lead ECGs will be collected at the time points specified in **Table 1**, Schedule of Events/Evaluations, after the patient has been in a supine, or if unable, semi-supine (no more than 45 degrees) position for a minimum of 5 minutes.

The 12-lead electrocardiogram includes standard PR, QRS, QT and QTc intervals as read by the ECG machine provided by the cardiac core lab. Fridericia's correction (i.e., QTcF) must be used for the correction of the QT interval.

A central ECG core lab will overread all ECGs and provide the final interpretation. At Screening the results will be available within 72 hours of the visit. At Baseline, the overread of the 3 serial ECGs will be available within 24 hours. The Investigator should use the ECG machine recorded QTcF value to determine patient eligibility.

The ICH guideline E14 (section 2.1.1) suggests excluding from early phase studies subjects who have marked baseline prolongation of the QT interval, namely those in whom QTc interval has repeatedly been demonstrated to be > 450 milliseconds (msec). Therefore, to be eligible for this study patients must meet exclusion criteria #14 based on QTcF intervals as assessed at the Screening and Baseline Visits.

At subsequent visits, if the QTcF interval is noted to be ≥ 450 msec (for male patients) or ≥ 470 msec (for female patients), it is recommended that the ECG be repeated at 10 minute intervals, for a total of 3 ECGs, to determine if the QTcF prolongation is a consistent finding. If the patient is observed to have a QTcF interval consistently ≥ 500 msec and/or a QTcF interval consistently increased by ≥ 60 msec compared to the average baseline QTcF interval, study drug

should be discontinued (see [Section 4.3.1, page 45](#)). The average baseline QTcF interval is defined as the average of the three QTcF interval values obtained at Visit 2.

The eligibility or continued participation in the trial of any patient with potentially significant ECG abnormalities should be discussed the Medical Monitor.

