	
randomized to SYN120 100 mg QD will receive two 10 mg tablets for the first 7 days, one placebo tablet and one 50 mg tablet for the next 7 days, and two 50 mg tablets every day for the remaining 14 weeks. Participants randomized to placebo will receive the same number of placebo tablets on the same titration schedule.
 
After randomization, patients will be evaluated at clinic visits at Week 4 (28 ± 3 days), Week 8 (56 ± 3 days), and Week 16 (112 ± 3 days), and again 2 weeks (14 ± 3 days) following the Week 16 Visit (or at Early Termination, if applicable). Patients will also be contacted by the study site by telephone at Week 2 (14 ± 3 days) and Week 12 (84 ± 3 days) for assessment of AEs.
 
At the clinic visits, patients will be asked to bring their study drug to the study site. Blood pressure and pulse (supine and standing) will be measured at each outpatient visit. Patients will be assessed for safety and tolerability in a blinded fashion regularly throughout the study and 2 weeks after their last dose of study drug.
 
Please refer to the Schedule of Events/Evaluations in Table 1 for specific timing of assessments.

Criteria for Withdrawal from Study	
Investigational medicinal product may be discontinued for a given participant at any time if clinically significant out-of-range laboratory values or clinically significant abnormal findings on physical examination or intolerable AEs put the patient at additional risk, as judged by the Investigator.
 
Patients will also discontinue IMP if their cognitive dysfunction or motor function worsens to the extent that in the judgment of the Investigator they require the addition of new medication to control their symptoms.
 
Patients may withdraw consent and discontinue from the study for any reason.
 
The Study Sponsor (Biotie Therapies) has the right to terminate the study at any time.
 
All patients who withdraw consent prematurely will be requested to return for an onsite visit that includes all safety procedures as outlined for early termination in Table 1. For any early discontinuation, the patient should be requested to return for a Safety Follow Up Visit 2 weeks after the last dose of study drug, unless the Early Termination Visit itself occurs 2 or more weeks after the last dose of study drug.

PROTOCOL SYNOPSIS	

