4.3 Criteria for Withdrawal from Study Drug or Study Participation

4.3.1 Study Drug Withdrawal

Investigators must contact the Medical Monitor to discuss any of the following events which may lead to the patient discontinuing study drug:

1. Patient is noncompliant with the study procedures or medications.
2. Patient takes prohibited concomitant medications as defined in this protocol or receives prohibited neurosurgical intervention for PD.
3. Patient has a clinically significant out-of-range laboratory value(s) or clinically significant abnormal finding(s) on physical examination or intolerable AEs (as determined by the patient) or that put the patient at additional risk as judged by the Investigator.
4. Patient's PDD symptoms worsen to the extent that, in the judgment of the Investigator, they require the addition of new anti-dementia medication or an increase in the dose of their concomitant cholinesterase inhibitor medication.

Any withdrawal of a patient from the study or discontinuation of study drug should be discussed with the Medical Monitor. Patients must discontinue study drug if any of the following events occur:

1. Patient develops an illness that would interfere with his or her continued participation.
2. Patient or caregiver (or legal representative, if applicable) withdraws consent.
3. There is confirmation of a pregnancy during the study, as evidenced by a positive pregnancy test.
4. The Sponsor/Sponsor's designee or a regulatory agency requests withdrawal of the patient.
5. The Sponsor or a regulatory agency terminates the study.

6. Patient has active suicidality since last visit as indicated by a positive response (“Yes”) to either Question 4 or Question 5 of the C-SSRS, or reports any suicidal behavior since their last C-SSRS assessment. The patient should be referred immediately to a Mental Healthcare Professional.
7. The patient has a QTcF interval consistently \geq 500 msec and/or a QTcF interval consistently increased by \geq 60 msec compared to the average baseline QTcF interval (see **Section 7.16**). The average baseline QTcF interval is defined as the average of the three QTcF interval values obtained at Visit 2. Fridericia’s method must be used for correction of QT intervals.
8. Investigators must follow guidelines provided related to monitoring hepatic parameters in relation to investigation guidelines and stopping rules. The following necessitate immediate cessation of dosing with IMP:

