6.2.5 Visit 4 (Week 4) Study Visit

Note: Confirm the arrangement for laboratory sample pick-up on the day of the Week 4 visit with the courier (see Central Laboratory Procedures Manual).

1. Assess AEs by asking open-ended queries and record the assessments.
2. Record concomitant medication use; assess and record any changes to anti-dementia or anti-Parkinson medication doses or regimens.
3. Obtain and record BP and pulse after at least 5 minutes supine rest and again after standing for approximately 1 and 3 minutes.
4. Perform physical and neurological exam.

5. Perform full UPDRS Parts I, II III (motor) and IV.

For patients with motor fluctuations: Perform full UPDRS Parts I, II III (motor) and IV, approximately 1 to 3 hours after the patient has taken a scheduled dose of levodopa (preferably their morning dose of levodopa). UPDRS in ON will be measured at a time representative of the ON state in that patient, not in “best” ON.

6. Administer C-SSRS.

7. Obtain 12-lead ECG and ensure the ECG is collected at a time when the patient is not experiencing dyskinesia that would interfere with an adequate recording.

8. Obtain samples for the following laboratory tests and record the date and time of collection:

a. Females of childbearing potential: Obtain urine hCG pregnancy test; verify method of contraception has not changed since Screening.

b. Hematology and chemistry (including liver function tests).

c. Blood sample for SYN120 plasma concentration [REDACTED]
[REDACTED] Obtain and record the date and time when the patient took the last dose of IMP. Record the date and time of SYN120 sample collection.

d. Blood sample for optional pharmacogenetic substudy (only if patient gave consent for the pharmacogenetic substudy and specimen was NOT collected during a previous visit): A single blood sample (approximately 10 mL) will be collected per patient. See **Section 7.13.**

e. Urine sample for urinalysis.

Note: For processing, labeling and shipping of samples, follow the instructions provided in the Central Laboratory Procedures Manual.

9. Obtain the returned blister cards dispensed at the Baseline Visit:

a. Assess and document the IMP accountability and compliance (document any missed dose(s), lost tablets and number of tablets taken).

b. Review and reconcile any discrepancies with the patient and caregiver.

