6.2.11.2 Optional Assessments for Unscheduled Visit

The following additional assessments may be performed at an Unscheduled Visit for assessment of an adverse event, at the Investigator's discretion, depending on the type of AE (e.g., an out-of-range lab value):

1. Obtain and record BP and pulse after at least 5 minutes supine rest and again after standing for approximately 1 and 3 minutes.
2. Obtain the 12-lead ECG and ensure the ECG is collected at a time when the patient is not experiencing dyskinesia that would interfere with an adequate recording. Assess any changes from Baseline for clinical significance.
3. Perform physical and neurological examination, and assess any changes from Baseline for clinical significance.
4. Administer C-SSRS if suicide risk concern.
5. Obtain samples for the following laboratory tests and record the date and time of collection:
 - a. Females of childbearing potential: Obtain urine hCG pregnancy test; verify method of contraception has not changed since Screening.
 - b. Hematology and chemistry (including liver function tests).

- c. Blood sample for SYN120 plasma concentration [REDACTED]
[REDACTED] Obtain and record the date and time when the patient took the last dose of IMP. Record the date and time of SYN120 sample collection.
- d. Urine sample for urinalysis.

Note: For processing, labeling and shipping of samples, follow the instructions provided in the Central Laboratory Procedures Manual.

6. In consultation with the Medical Monitor, discuss any other appropriate diagnostic tests required to evaluate patient's AE.
7. Re-dispense remaining unused blister cards collected from the patient to continue IMP dosing to the next scheduled visit (if applicable).
8. Complete eCRF information in the designated modules.

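### The repeat-ECG trigger in Protocol 7.16 uses absolute QTcF only, so a rise of ≥ 60 msec from a low baseline, a mandatory stop if consistent, can go unconfirmed until the next scheduled visit

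*Protocol*

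**What the plan says.** The stopping rule is in Protocol 4.3.1. The list that contains item 7 opens with "Patients must discontinue study drug if any of the following events occur". Item 7 has two arms: QTcF consistently at or above 500 msec, "and/or a QTcF interval consistently increased by" 60 msec or more relative to the mean of the three Visit 2 readings. Section 7.16 repeats both arms.

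The confirmation step appears in 7.16 only. Its trigger for visits after Baseline reads: "if the QTcF interval is noted to be ≥ 450 msec (for male patients) or ≥ 470 msec (for female patients), it is recommended". The action advised is two further recordings, 10 minutes apart, making three in all. The purpose is given as "to determine if the QTcF prolongation is a consistent finding".

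ECGs under treatment are scheduled at "Week 4 (28 ± 3 days), Week 8 (56 ± 3 days), and Week 16 (112 ± 3 days"). Table 1 specifies triplicate recordings at Baseline only. The Week 4 instruction in 6.2.5 is for one recording: "Obtain 12-lead ECG and ensure the ECG is collected at a time when the patient is not experiencing dyskinesia". Weeks 8 and 16 are worded the same way. Exclusion criterion 14 sets upper limits on baseline QTcF and no lower limit.

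**The concern.** Both arms of the stopping rule depend on the word 'consistently', so a single reading does not clearly satisfy either. The step that settles consistency is triggered by an absolute value, while one arm of the rule is a change from baseline. For patients who start low, a rise large enough to require stopping can stay under the trigger.

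The mismatch also runs the other way. A man with a baseline of 445 who reads 452 has risen 7 msec and is prompted for repeats. A man with a baseline of 380 who reads 445 has risen 65 msec and is not.

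What is at stake is patient safety under the protocol's own rule: continued dosing at 100 mg daily with a possible stop criterion unconfirmed. No efficacy endpoint or analysis is affected.

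**Working it through.** There is no plan figure to reproduce here. The check compares thresholds and visit days.

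**Inputs.** Repeat trigger T: 450 msec (men), 470 msec (women), Protocol 7.16. Change-from-baseline stop: 60 msec, Protocol 4.3.1 item 7 and 7.16. Visit days 28, 56 and 112, each ± 3: Synopsis, Overview of Study Procedures.

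**Step 1: the ≥ 500 msec arm.** 500 exceeds both 450 and 470, so every such reading prompts repeats. There is no gap in this arm.

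**Step 2: the ≥ 60 msec arm.** With baseline B, a rise of exactly 60 msec prompts repeats only if B + 60 ≥ T, that is B ≥ T − 60.
- Men: 450 − 60 = 390 msec.
- Women: 470 − 60 = 410 msec.

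Below these baselines some qualifying rises go unprompted. The largest whole-msec rise missed is (T − 1) − B:

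| Baseline, men | Baseline, women | Largest unprompted rise | Unprompted range |
|---|---|---|---|
| 380 | 400 | 449 − 380 = 469 − 400 = 69 | 60–69 msec |
| 370 | 390 | 449 − 370 = 469 − 390 = 79 | 60–79 msec |
| 360 | 380 | 449 − 360 = 469 − 380 = 89 | 60–89 msec |

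**Step 3: time to the next scheduled ECG.**
- Week 4 to Week 8: nominally 56 − 28 = 28 days. With windows, (56 − 3) − (28 + 3) = 22 days to (56 + 3) − (28 − 3) = 34 days.
- Week 8 to Week 16: nominally 112 − 56 = 56 days. With windows, (112 − 3) − (56 + 3) = 50 days to (112 + 3) − (56 − 3) = 62 days.
- Week 16 is the end of dosing, so a rise first seen there does not lead to continued exposure.

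The Week 2 and Week 12 contacts are telephone calls and add no ECG.

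**Step 4: does other text supply the prompt?**
- Unscheduled visits (6.2.11.2): "additional assessments may be performed at an Unscheduled Visit for assessment of an adverse event", at the investigator's discretion. The ECG there is optional.
- Core-lab overread (7.16): it covers all ECGs, but a turnaround is stated only for Screening (72 hours) and Baseline, where "At Baseline, the overread of the 3 serial ECGs will be available within 24 hours". No repeat is tied to it.
- Medical Monitor (7.16): potentially significant ECG abnormalities are to be discussed. There is no numeric trigger and no request for a repeat.
- Safety Data Monitor (Protocol 8.8; quarterly review in SAP 3.7): periodic review, which is not same-visit confirmation.

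**Step 5: how many patients have a baseline in this zone?** The documents give no baseline QTcF distribution, so this cannot be determined. As an assumption only, take a normal distribution with mean m of 400–420 msec and SD s of 15–25 msec, truncated at the entry limit. The share below the cut-off is Φ((T − 60 − m)/s) / Φ((T − m)/s). Over those ranges it runs from about 2% to 35% in men and 25% to 75% in women. That is the share whose baseline is low enough for a 60 msec rise to be missed. It is not the share expected to have such a rise.

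**The case against.** The strongest reply is that the ≥ 60 msec rule is mandatory and stands on its own. It applies at every baseline and defines its own reference value, so a site must compare each reading with the Visit 2 average in order to comply. Because the rule requires consistency, a reading 60 msec above baseline cannot be resolved without another ECG, and the rule therefore implies the repeat. The 450/470 sentence is an added recommendation and is not worded as the exclusive route.

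Backstops also exist. A reading at the protocol's own stopping magnitude is hard to regard as anything other than potentially significant, so 7.16 would send it to the Medical Monitor. An unscheduled visit can be held at any time at the investigator's discretion, and a marked QTcF rise could itself be recorded as an adverse event that justifies an ECG. Core-lab alert procedures may exist outside these documents. All affected readings lie below 450 msec (men) or 470 msec (women), which are the entry limits, and no frequency is shown.

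Much of this stands as a limit on the claim. An attentive investigator may well repeat the ECG, and the delays in Step 3 assume that nobody does. But none of the backstops asks for a same-visit repeat or carries a numeric trigger. Where the protocol does state a trigger, it leaves out part of the range its stopping rule covers, and an implied repeat is weaker than a stated one.

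**Conclusion.** The concern holds. The stated confirmation step does not cover the whole range of the mandatory stopping rule. It misses some rises of ≥ 60 msec in men with a Visit 2 average below 390 msec and in women below 410 msec. If no one acts on judgment, the wait for the next scheduled ECG is 22–34 days after Week 4 or 50–62 days after Week 8, with dosing continuing.

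This describes what the text permits and does not predict what sites will do. The ≥ 500 msec arm is unaffected, as are rises from higher baselines and readings at Week 16. The number of patients and events involved is unknown. Because the gap bears on a mandatory safety rule and is cheap to close, it should be fixed.

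**What to change.** In Protocol 7.16, extend the repeat trigger to: QTcF ≥ 450 msec (men) or ≥ 470 msec (women), or ≥ 60 msec above the average baseline QTcF. Leave the stopping thresholds in 4.3.1 item 7 and 7.16 unchanged, and send sites a short note. Every reading that could meet the stopping rule would then prompt three ECGs at the same visit.

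The cost is one clause plus, for each patient with such a reading, two further ECGs at 10-minute intervals (2 × 10 = 20 minutes). The repeats also protect a patient from being stopped on one noisy reading. They would remain a recommendation, as they are now above 450/470 msec, so the change supplies the prompt but does not guarantee the confirmation.
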